9.4.4 Vital signs

Where supine blood pressure and pulse rate are measured in triplicate, the mean value will be calculated and used in all subsequent calculations. When triplicate blood pressure or pulse rate measurements precede a standing measurement, the last supine blood pressure or pulse rate measurement will be used for orthostatic calculations.

Vital signs data will be summarized by treatment in separate outputs for each population (Japanese, Caucasian), as well as for each sex within population, together with changes from baseline.

Baseline is defined as follows:

For supine parameters, baseline is the mean of the average values of the triplicate assessments collected at -1 hour, -0.5 hours, and predose on Period 1. All other time points are considered as post baseline, including predose on Periods 2 and 3.

For standing parameters, baseline is the mean of the assessments collected at -1 hour, -0.5 hours, and predose on Period 1. All other time points are considered as post baseline, including predose on Periods 2 and 3.

For orthostatic parameters, baseline is the mean of -1 hour (standing - last supine), -0.5 hours (standing - last supine), and predose (standing - last supine) assessments on Period 1. The other time points are considered as post baseline, including predose on Periods 2 and 3. Here "last supine" means the last supine value taken prior to the standing value.

Figures of mean vital signs and mean changes from baseline profiles will be presented by treatment over time in separate outputs for each population (Japanese, Caucasian), as well as for each sex within population. Furthermore, values for individual subjects will be listed.

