**Treatment Arms and Planned Duration for an Individual Subject:**

Subjects will participate in: a screening period of up to 27 days; 3 treatment periods, each of either 4 days (Period 1) or 3 days (Periods 2 and 3) duration; and a follow-up period of up to 10 days. The total study duration for each subject will be up to 47 days.

Cohorts 1 and 3: Subjects will receive a single dose of 50 mg lasmiditan or placebo in Period 1, 100 mg lasmiditan or placebo in Period 2, and 200 mg lasmiditan or placebo in Period 3.

Cohort 2: Subjects will receive single dose of 50, 100, or 200 mg lasmiditan or placebo in Period 1, 400 mg lasmiditan or placebo in Period 2, and 2 doses of 200 mg lasmiditan or 2 doses of placebo administered 2 hours apart in Period 3.

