## 2. Schedule of Activities

## Study Schedule Protocol H8H-JE-LAIE

	Screening	Period 1			Period 2			Period 3			Follow-up/ED	Comments
		Day										
Procedure	-28 to -2 days prior to Day 1 of Period 1	-1	1	2	3	1	2	3	1	2	3	7 to 10 days following Day 3 of Period 3
Informed Consent	X											
Subject Admission to CRU		X										
Subject Discharge from CRU										X		
Chest X-ray	X											
Enrollment/ Randomization		X										
Lasmiditan Administration		X			X			X a				A washout of approximately 72 hours between doses across periods
Medical History	X	X										Interim medical history only on Day -1
Urine Drug Screen	X	X										
Alcohol Test		X										
Height	X											
Body Weight	X	X									X	
Triplicate Vital Signs (supine)	X	-1, -0.5, P, 0.5, 1, 1.5, 2, 2.5, 3, 4, 6, 8, 12	24, 36	48	P, 0.5, 1, 1.5, 2, 2.5, 3, 4, 6, 8, 12	24, 36	48	P, 0.5, 1, 1.5, 2, 2.5, 3, 3.5 b , 4, 4.5 b , 5 b , 6, 8, 12	24, 36	48	X	Time points relative to the time of investigational product administration in each period and shown in hours. For repeated doses, timepoints relative to the first dose. Single vital signs only at follow-up/ED. Time points may be added, if warranted and agreed by Lilly and the investigator
Single Orthostatic Vital Signs	X	-1, P, 1, 2, 3, 4, 6, 8, 12	24, 36	48	P, 1, 2, 3, 4, 6, 8, 12	24, 36	48	P, 1, 2, 3, 4, 6, 8, 12	24, 36	48	X	Time points relative to the time of investigational product administration in each period. For repeated doses, time points relative to the first dose. Time points may be added if warranted and agreed by Lilly and the investigator
Clinical Laboratory Tests	X	P			P			P			X	See Appendix 2 , Clinical Laboratory Tests, for details

	Screening	Period 1			Period 2			Period 3			Follow-up/ED	Comments	
		Day											
Procedure	-28 to -2 days prior to Day 1 of Period 1	-1	1	2	3	1	2	3	1	2	3	7 to 10 days following Day 3 of Period 3	
Adverse Event Review	X	X	X	X	X	X	X	X	X	X	X	X	
Pregnancy Test	X	X									X	Serum pregnancy test for all females	
Follicle-stimulating hormone	X												Postmenopausal females only
Physical Examination	X	X			X			X			X	X	Full physical examination performed at screening. At other time points, symptom-directed physical examination only

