#### 3.2. Background

Lasmiditan has a chemical structure and pharmacological profile that is distinct from triptans, which are the current standard of care for the treatment of acute migraine. It does not contain the indole group found in all triptans, but instead has a pyridinoyl-piperidine scaffold that is unique to antimigraine medications. Lasmiditan is a low-molecular weight agonist of the 5-HT1F receptor with a nonvascular and primarily neural mechanism of action. It has a high affinity for the human 5-HT1F receptor and a >470-fold selectivity for the human 5-HT1F receptor relative to the 5-HT1B receptor.

Lasmiditan doses of 0.1 to 400 mg have been evaluated in healthy subjects or patients with migraine across completed Phase 1, 2, and 3 clinical studies. The most frequently reported lasmiditan treatment-emergent adverse events (TEAEs) in the two Phase 3, placebo-controlled studies in which patients treated 1 migraine attack with oral lasmiditan (50, 100, or 200 mg) or placebo were dizziness, paresthesia, somnolence, fatigue, lethargy, and nausea, and the majority were mild or moderate in severity. Safety and tolerability in healthy subjects were similar up to 400 mg, with tiredness, drowsiness, dizziness, and paresthesia being the most frequently reported adverse events (AEs). The majority of these were mild in severity, and none were severe. In healthy subjects, peak plasma concentrations of lasmiditan were observed approximately 1.5 to 2.5 hours after a single oral dose ranging from 25 to 400 mg, and the geometric mean terminal half-life was approximately 4 hours. Lasmiditan PK was approximately dose linear. There was an increase of approximately 20% to 30% in maximum observed plasma concentration (Cmax) and a 30% increase in area under the concentration versus time curve (AUC) in female subjects in a previous study.

Following oral dosing with lasmiditan, up to 16 metabolites, including 3 major metabolites (M7, M8, and M18), were detected in human plasma and urine. These metabolites lacked significant pharmacological activity at the 5 HT1F receptor and were generally considered to be pharmacologically inactive. The relative proportions of metabolites to intact lasmiditan remained reasonably constant throughout the oral dose range studied and their PK was approximately linear. The half-life of the metabolites ranged from approximately 4.5 to 21 hours.

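### The single Period 1 baseline carries any between-period drift into the tabulated vital-sign changes by dose, fully in Cohort 3 and partly in Japanese subjects; a same-period predose change should be added

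*SAP*

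**What the plan says.** SAP 9.4.4 takes one baseline per subject, from the readings before the first dose in Period 1. For supine and for standing values it adds: "All other time points are considered as post baseline, including predose on Periods 2 and 3". For orthostatic differences the rule is the same: "The other time points are considered as post baseline, including predose on Periods 2 and 3".

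The same section summarises values and changes by treatment within each population, and by sex within population. It also plans plots: "Figures of mean vital signs and mean changes from baseline profiles will be presented by treatment over time". It has no period term and no by-period table. SAP section 6 gives Placebo and 2 x Placebo as separate treatments. SAP 9.4.9 plans no inferential safety analysis.

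On dose order in Cohorts 1 and 3, the protocol synopsis states: "Subjects will receive a single dose of 50 mg lasmiditan or placebo in Period 1, 100 mg lasmiditan or placebo in Period 2". Period 3 is 200 mg or placebo. Cohort 2 receives 50, 100 or 200 mg or placebo in Period 1, 400 mg or placebo in Period 2, and two doses of 200 mg or of placebo in Period 3.

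The Schedule of Activities has predose vital signs, supine and orthostatic, in every period. The supine row for Period 2 reads "P, 0.5, 1, 1.5, 2, 2.5, 3, 4, 6, 8, 12", where P is predose.

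**The concern.** The dose rises with period, and the change score runs back to Period 1. Anything that shifts blood pressure or pulse between dosing days, whatever its cause, enters the change for the later doses and not for the first. Subjects are resident throughout, with doses about 72 hours apart, so dosing falls on about days 1, 4 and 7 of the stay.

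Vital signs are one of the protocol's named means of assessing safety. The by-treatment mean changes are what a reader will compare across doses and with placebo. In Cohort 3 a steady drift with no drug effect would look like a dose trend. It would also enter a same-dose comparison of Japanese with Caucasian subjects, because the two populations receive 100 and 200 mg in different mixes of periods.

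**Working it through.** **1. Subject counts.** Protocol 5.2 and SAP section 7 plan about 2 completers per sequence. Japanese: 2 x (3 + 4) = 14. Caucasian: 2 x 4 = 8. Both match the plan.

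**2. Drift carried by each treatment.** Assume no drug effect and a linear drift of d per period. Under the Period 1 baseline a change in period k carries (k - 1) x d. Averaging over the subjects on each treatment, counted from the sequence tables (Protocol 5.1, SAP section 5) at 2 per sequence:

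| Population | Treatment | Subjects in Periods 1/2/3 | Drift carried | Minus Placebo |
|---|---|---|---|---|
| Caucasian | 50 mg | 6/0/0 | 0 | -d |
| Caucasian | 100 mg | 0/6/0 | d | 0 |
| Caucasian | 200 mg | 0/0/6 | 2d | +d |
| Caucasian | Placebo | 2/2/2 | (2 x 1 + 2 x 2)/6 = d | – |
| Japanese | 50 mg | 6/0/0 | 0 | -0.80d |
| Japanese | 100 mg | 2/4/0 | 4/6 = 0.67d | -0.13d |
| Japanese | 200 mg | 2/0/4 | 8/6 = 1.33d | +0.53d |
| Japanese | 400 mg | 0/6/0 | 1.0d | +0.20d |
| Japanese | Placebo | 4/4/2 | (4 + 4)/10 = 0.8d | – |
| Japanese | 2 x 200 mg | 0/0/6 | 2d | see below |
| Japanese | 2 x Placebo | 0/0/2 | 2d | see below |

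2 x 200 mg minus 2 x Placebo is 2d - 2d = 0.

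200 mg minus 50 mg carries 2d in Caucasian and 1.33d in Japanese subjects. If d is the same in both, Caucasian minus Japanese at a given dose carries d - 0.67d = 0.33d at 100 mg and 2d - 1.33d = 0.67d at 200 mg.

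**3. Size for an assumed drift.** For d of 1 to 3 mmHg or beats per minute in either direction, 200 minus 50 mg is off by 2 to 6 units in Caucasian and by 1.3 to 4.0 units in Japanese subjects. With each period's own predose value as baseline, a shift already present before dosing cancels in every row.

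**4. Is the later predose value free of earlier dosing?** Protocol 3.2 says that "the geometric mean terminal half-life was approximately 4 hours", so 72/4 = 18 half-lives pass between doses. The longest metabolite half-life given is 21 hours (72/21 = 3.4 half-lives), but the protocol describes the metabolites as generally considered inactive.

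**5. Precision, 200 minus 50 mg in Cohort 3.** Assume an SD of 4 for a time-point value and s between days; neither is in the documents. The supine Period 1 baseline averages three time points, so its error variance is 16/3 = 5.33. Six subjects receive each dose, and four (sequences 2 and 4) receive both.

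- Period 1 baseline: variance = [6(2s² + 16 + 5.33) + 6(16 + 5.33) - 2 x 4 x 5.33]/36. For s = 3 this is 321.3/36 = 8.93, SD 2.99. For s = 0 it is 213.3/36 = 5.93, SD 2.43.
- Same-period baseline, three time points in Period 1 and one in Period 3: variance = (16 + 5.33)/6 + (16 + 16)/6 = 8.89, SD 2.98 whatever s is.
- Same-period baseline, one predose time point in Period 1 as well: variance = 64/6 = 10.67, SD 3.27.

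The price therefore depends on day-to-day variation: none at s = 3, and an SD of 2.98 against 2.43 if there is no such variation.

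**The case against.** A reader might infer that any drift over the stay will be reported as a dose effect, and that the planned outputs cannot separate the two. The documents do not support that.

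- Predose in Periods 2 and 3 is kept as a time point in each treatment's profile, so drift present before dosing is visible. If the same subjects contribute, mean postdose change minus mean predose change equals the mean change from same-period predose. Only its SD cannot be recovered from the summaries.
- Placebo is randomised into every period. 2 x 200 mg against 2 x Placebo is period-matched, and 100 mg against placebo in Cohort 3 is also balanced under linear drift.
- Cohort 2 gives 100 and 200 mg in Period 1, so Japanese confounding is partial, and 400 mg carries less drift than 200 mg.
- Starting caffeine and tobacco abstinence is not a ready cause of drift. Protocol 6.3.2 begins both 48 hours before admission, and so before the Period 1 baseline.
- The primary endpoint is the incidence of adverse events, which this baseline does not touch. The vital-sign output is descriptive.
- A baseline before any dose is legitimate, SAP version 2 clarified it deliberately, and it alone shows cumulative change over the stay.

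All of this stands, and it argues against replacing the Period 1 baseline. It does not correct the tabulated postdose changes. The by-treatment tables still contain the drift, and no same-period placebo comparison is planned.

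**Conclusion.** The point holds as a limited one about descriptive tables. In Cohort 3 the tabulated changes for 50, 100 and 200 mg carry 0, d and 2d against d for pooled placebo. In Japanese subjects the distortion is smaller and does not rise steadily with dose, and the repeated-dose comparison is clean. Subject-specific shifts between days also enter the SDs, and in columns that mix periods a common drift widens them further.

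This rests on linear drift, about 2 completers per sequence, and a d that the documents do not give; if d is near zero, nothing is lost. A same-period baseline removes only what is present before dosing. It does not remove a period effect on the postdose course, nor undo the link between dose and period in the raw values. The case for the change is that the readings are already scheduled and the addition is cheap. The planned baseline is not invalid.

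**What to change.** In SAP 9.4.4, for supine, standing and orthostatic parameters, add by-treatment tables and figures of change from the predose value of the same period. In Period 1 use the mean of the scheduled pre-dose readings. State that these outputs are the ones to use when comparing doses, or a dose with placebo. Keep the Period 1 baseline outputs to show cumulative change over the stay.

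The wording for Period 1 needs care. SAP 9.4.4 names a -0.5 hour reading for standing and orthostatic values, but the Schedule of Activities has orthostatic vital signs only at -1 hour and predose; the two should be reconciled.

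Cost: one derived variable and a further set of outputs. The baseline in Periods 2 and 3 rests on one time point, in triplicate for supine values and a single reading for standing, so it is noisier when day-to-day variation is small. No new measurements are needed.

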9.4.5 Electrocardiogram (ECG)

The ECG data will be obtained directly from the 12-lead ECG traces. These data include the PR and QT intervals, QRS duration and heart rate. In addition, QTcF (the QT interval corrected using Fridericia's formula) will be calculated as follows:

$$QTcF = \frac{QT}{\sqrt[3]{(60/HR)}}$$

The ECG data will be listed and summarized by population and treatment, together with changes from baseline, where baseline is defined as the mean of the average values of the triplicate assessments collected at -1 hour, -0.5 hours, and predose on Period 1. All other time points are considered as post baseline, including predose on Periods 2 and 3.

Figures of mean ECG data and mean changes from baseline will be presented by population and treatment. The frequency of subjects with a maximum increase from baseline in QTcF interval will be summarized by population and treatment according to the following categories: >30 ms and >60 ms. In addition, the frequency of subjects with QTcF postdose values, according to the following categories: >450 ms, >480 ms and >500 ms, will be summarized by population and treatment.

The relationship between concentrations of lasmiditan and changes from baseline QTcF (Δ QTcF) will be explored graphically, using different symbols and colours for each group. The comparisons to be explored are:

- Japanese vs Caucasian
- Japanese (Male vs Female)
- Caucasian (Male vs Female)

A linear mixed-effects model will be fitted with the change from baseline in QTcF (Δ QTcF) as the response, the time-matched concentration as a covariate, population or sex and time-matched concentration-by-population (or sex) as fixed effects for the population or sex analysis respectively, and subject as a random effect. Population and sex will be fitted as binary variables, as appropriate (0=Caucasian, 1=Japanese, 0=Male, 1=Female accordingly). The intercept, slope, and random effect covariance from the model along with their 90% CI will be reported. If the model fails to converge, alternative models will be tested. A scatter plot of Δ QTcF versus the concentrations with the fitted lines will also be plotted. Additional analysis may be performed, if deemed necessary.

Example SAS Code:

```
proc mixed data=ecg alpha=0.1;
  class usubjid effect;
  model chg_qtcf = conc + effect + conc*effect / alpha=0.1 cl solution
  residual ddfm=bw;
  random intercept conc / subject=usubjid type=un s;
run;
```

where effect represents “population” for the comparison of Japanese versus Caucasian, and “sex” for the comparison of males versus females within each population.

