Triplectate 12-lead Electrocardiogram	X	-1, -0.5, P, 1, 1.5, 2, 2.5, 3, 4, 6, 8, 12	24, 36	48	P, 1, 1.5, 2, 2.5, 3, 4, 6, 8, 12	24, 36	48	P, 1, 1.5, 2, 2.5, 3, 4, 6, 8, 12	24, 36	48	X	Time points relative to the time of investigational product administration in each period. For repeated doses, time points relative to the first dose. Refer to Section 9.4.4. Performed after subject has rested in supine position for ~5 to 10 minutes. On days without dosing, should be performed close to the Day 1 dosing time, when possible. Collected in triplicate except at screening and follow-up/ED	
Columbia-Suicide Severity Rating Scale/Self-Harm	X	X									X	X	
Genetic Sample			X										Period 1 only
Blood Sample for Lasmiditan and Metabolites Pharmacokinetics		P, 0.5, 1, 1.5, 2, 2.5, 3, 4, 6, 8, 12	24, 36	48	P, 0.5, 1, 1.5, 2, 2.5, 3, 4, 6, 8, 12	24, 36	48	P, 0.5, 1, 1.5, 2 c , 2.5, 3, 3.5 b , 4, 4.5 b , 5 b , 6, 8, 12	24, 36	48			Time points relative to the time of investigational product administration in each period. For repeated doses, time points relative to the first dose

Abbreviations: CRU = clinical research unit; ED = early discontinuation; P = predose.

Note: if multiple procedures take place at the same time point, the following order of the procedure should be use: electrocardiogram, vital signs, and venipuncture.

- a Subjects in Period 3 of Cohort 2 will receive 2 doses separated by 2 hours.
- b Subjects in Period 3 of Cohort 2 only.
- c For subjects in Period 3 of Cohort 2, pharmacokinetic sample collected prior to second dose.

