**Table LAIE.5.3. Treatment Sequences for Cohort 2; Japanese Subjects**

Treatment Sequence	Period 1	Period 2	Period 3 a
1	Placebo	400 mg lasmiditan	2 $\times$ 200 mg lasmiditan
2	50 mg lasmiditan	Placebo	2 $\times$ 200 mg lasmiditan
3	100 mg lasmiditan	400 mg lasmiditan	2 $\times$ placebo
4	200 mg lasmiditan	400 mg lasmiditan	2 $\times$ 200 mg lasmiditan

a Doses administered 2 hours apart.

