## 6.2. Exclusion Criteria

Subjects will be excluded from study enrollment if they meet any of the following criteria at screening and/or enrollment:

- [8] are investigative site personnel directly affiliated with this study and their immediate families. Immediate family is defined as a spouse, biological or legal guardian, child, or sibling.
- [9] are Lilly or Covance employees
- [10] are currently enrolled in a clinical study involving an investigational product or any other type of medical research judged not to be scientifically or medically compatible with this study.
- [11] have known allergies to lasmiditan, related compounds or any components of the formulation of lasmiditan

- [12] have previously received the investigational product in this study, withdrawn from this study, or received lasmiditan in any other study investigating lasmiditan
- [13] have participated (dosed with investigational product), within the last 30 days, in a clinical study involving an investigational product. If the previous investigational product has a long half-life, 5 half-lives or 30 days (whichever is longer) should have passed
- [14] have a history of, or ECG findings of, clinically significant bradycardia, heart block, tachycardia, sick sinus syndrome/sinoatrial block, or second or third-degree atrioventricular block, or have any other abnormality in the 12-lead ECG that, in the opinion of the investigator, confounds assessment of QT interval
- [15] have an abnormal supine blood pressure (defined as systolic blood pressure <95 or >140 mmHg or diastolic blood pressure <65 or >90 mmHg) at screening. After screening, additional assessments may be performed to confirm eligibility
- [16] have a history of syncope, presyncope, uncontrolled vertigo, postural dizziness, or a risk of falls, as judged to be clinically significant by the investigator, or have orthostatic decreases in supine blood pressure of >20 mmHg, or have orthostatic decreases in diastolic blood pressure of >10 mmHg at screening. Measurements of orthostatic blood pressure may be repeated if asymptomatic
- [17] have an estimated glomerular filtration rate (eGFR) of <60 mL/min/1.73 m^2 as assessed using the Chronic Kidney Disease Epidemiology Collaboration formula (Section 9.4.1.1)

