5. STUDY DESIGN

This is a randomized, 3-period, subject- and investigator-blind, crossover study in healthy Japanese and Caucasian subjects.

Subjects will be evaluated for study eligibility ≤ 28 days prior to enrollment. Subjects who fulfil the eligibility criteria will be admitted to the clinical research unit (CRU) on Day -1 in Period 1 (the day before their first dose of lasmiditan or placebo).

Subjects will be enrolled into 1 of 3 cohorts. Within each cohort, subjects will be randomized to a treatment sequence, as indicated in Table 1, Table 2, and Table 3. Randomization will be stratified by sex, such there will be an approximately equal number of male and female subjects in each cohort.

Table 1. Treatment Sequences for Cohort 1; Japanese Subjects

Treatment Sequence	Period 1	Period 2	Period 3
1	Placebo	100 mg lasmiditan	200 mg lasmiditan
2	50 mg lasmiditan	Placebo	200 mg lasmiditan
3	50 mg lasmiditan	100 mg lasmiditan	Placebo

Table 2. Treatment Sequences for Cohort 2; Japanese Subjects

Treatment Sequence	Period 1	Period 2	Period 3 ^a
1	Placebo	400 mg lasmiditan	2 x 200 mg lasmiditan
2	50 mg lasmiditan	Placebo	2 x 200 mg lasmiditan
3	100 mg lasmiditan	400 mg lasmiditan	2 x placebo
4	200 mg lasmiditan	400 mg lasmiditan	2 x 200 mg lasmiditan

^a Doses administered 2 hours apart

Table 3. Treatment Sequences for Cohort 3; Caucasian Subjects

Treatment Sequence	Period 1	Period 2	Period 3
1	Placebo	100 mg lasmiditan	200 mg lasmiditan
2	50 mg lasmiditan	Placebo	200 mg lasmiditan
3	50 mg lasmiditan	100 mg lasmiditan	Placebo
4	50 mg lasmiditan	100 mg lasmiditan	200 mg lasmiditan

After randomization on Day 1, investigational medical product will be administered orally on the morning of Day 1 after an overnight fast of at least 8 hours. Blood samples will be collected for PK analysis predose, and for up to 48 hours postdose in each period. There will be a washout period of approximately 72 hours between dose administrations across periods.

Subjects will be discharged from the CRU following completion of all scheduled procedures on Day 3 of Period 3, as defined in the Schedule of Activities (Section 2 in the protocol), and will attend a follow-up visit 7 to 10 days following discharge from the CRU on Day 3 of Period 3.

Safety and tolerability will be assessed throughout the study by means of an adverse event (AE) review, physical examinations, body weight, vital sign measurements, 12-lead

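### The QTcF >450/480/500 ms counts take no account of the subject's own baseline, so a pre-existing high value can be tabulated under lasmiditan; a cheap improvement, not a stated error

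*SAP*

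**What the plan says.** SAP 9.4.5 defines two categorical QTcF summaries.

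- **Absolute values:** "the frequency of subjects with QTcF postdose values, according to the following categories: >450 ms, >480 ms and >500 ms", by population and treatment. No condition on the baseline value is attached.
- **Change:** "The frequency of subjects with a maximum increase from baseline in QTcF interval will be summarized by population and treatment", in the categories >30 ms and >60 ms. Unlike the absolute count, this sentence does not confine itself to postdose readings.

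One baseline serves all three periods: "the mean of the average values of the triplicate assessments collected at -1 hour, -0.5 hours, and predose on Period 1". The section then adds: "All other time points are considered as post baseline, including predose on Periods 2 and 3".

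At entry, Protocol 6.2 criterion [14] lists certain rhythm and conduction findings and then excludes candidates who "have any other abnormality in the 12-lead ECG that, in the opinion of the investigator, confounds assessment of QT interval". No criterion gives a QTcF value in milliseconds. SAP 9.4.1 has a treatment-emergence rule for adverse events (new, or worse after dosing); section 9.4.5 has no counterpart for ECG values.

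**The concern.** A table of subjects above 450 ms by treatment invites the reader to compare lasmiditan columns with placebo. If a subject was above 450 ms before any dose, the entry under lasmiditan describes the subject and not the drug. With about six subjects per active column, one such person supplies a 17% cell. If that person is in a sequence with no placebo period, the placebo column shows nothing to set against it.

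The protocol includes 400 mg partly to look at the QT interval (sections 5.4 and 5.5), so this table will be read closely.

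The change table raises a smaller issue. Read literally, a reading taken before the Period 2 or Period 3 dose is post baseline and could supply the maximum increase for the treatment that had not yet been given.

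**Working it through.** **1. Column sizes.** Inputs: the sequence tables (SAP Tables 1 to 3) and about 2 completers per sequence (SAP section 7). Japanese: 2 x (3 + 4) = 14. Caucasian: 2 x 4 = 8. Both match the SAP.

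| Treatment | Japanese sequences | n | Caucasian sequences | n |
|---|---|---|---|---|
| Placebo | 5 | 10 | 3 | 6 |
| 2 x placebo | 1 | 2 | none | 0 |
| 50 mg | 3 | 6 | 3 | 6 |
| 100 mg | 3 | 6 | 3 | 6 |
| 200 mg | 3 | 6 | 3 | 6 |
| 400 mg | 3 | 6 | none | 0 |
| 2 x 200 mg | 3 | 6 | none | 0 |

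Check: 42 = 14 x 3 and 24 = 8 x 3. SAP section 6 lists placebo and 2 x placebo as separate treatments.

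**2. What one subject with baseline above 450 ms adds, if counted in every period.**

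- Cohort 2 sequence 4: 1/6 = 16.7% at each of 200 mg, 400 mg and 2 x 200 mg; 0/10 on placebo.
- Cohort 3 sequence 4: 1/6 at each of 50, 100 and 200 mg; 0/6 on placebo.
- Cohort 2 sequence 3: 1/6 at 100 and 400 mg; 1/2 on 2 x placebo; 0/10 on placebo.
- Cohort 2 sequence 1: 1/6 at 400 mg and 2 x 200 mg; 1/10 on placebo.
- Cohort 3 sequence 1: 1/6 at 100 mg, 200 mg and placebo alike.

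Two of the 11 sequences contain no placebo of either kind: 2 x 2 = 4 of 22 completers (18%).

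**3. How sure the count is.** Each period has 12 postdose ECG times: nine from 1 to 12 h, then 24, 36 and 48 h. For a true mean m and within-subject SD s, with independent readings and no drug effect, the chance of at least one value above 450 ms is 1 - Phi((450 - m)/s)^12. The documents give no SD, so 5 to 10 ms is assumed. A simulation repeats this with half the variance shared within a period.

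| True mean | Independent, one period | Shared variance, one period | Shared variance, all three periods |
|---|---|---|---|
| 448 ms | 99.4 to 99.9% | 82 to 88% | 55 to 68% |
| 450.1 ms | 99.98% | about 93% | 79 to 80% |
| 455 ms | about 100% | 98 to 99.6% | 94 to 99% |

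**4. The maximum increase.** Periods 2 and 3 each have 13 readings, of which one is predose. With a washout of about 72 h and a half-life of about 4 h (Protocol 3.2), the lasmiditan left at that reading is 0.5^(72/4) = 0.5^18, or about 0.0004%. For the longest metabolite half-life, 21 h, it is 0.5^(72/21) = 9.3%. Period 1 is unaffected, because its predose readings form the baseline.

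Simulated chance of a maximum increase above 30 ms with no drug effect (independent readings; baseline the mean of three):

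| Assumed SD | Predose included | Postdose only |
|---|---|---|
| 5 ms | about 0 | about 0 |
| 8 ms | 0.74% | 0.68% |
| 10 ms | 5.3% | 4.9% |

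The largest difference is about 0.4 percentage points, or 6 x 0.004 = 0.02 subjects in a column of six.

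**The case against.** The case for leaving the text alone has real force.

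- **Placebo usually exposes the pattern.** Nine of the 11 sequences include placebo or 2 x placebo, so most baseline-high subjects would show there too. This stands, and confines the worst case to about 4 of 22 subjects.
- **Other outputs guard against misreading.** ECG values are listed, changes from baseline are summarized and plotted, and the >30/>60 ms table is referenced to baseline. With 22 subjects a high baseline can be traced individually. This stands, but the listings do not alter what the threshold table reports.
- **The main QT analysis is untouched.** The relationship named in Protocol 10.3.1.2 and modelled in SAP 9.4.5 has change from baseline as its response. This stands.
- **The trigger may never occur.** Subjects are healthy, ECG-screened and subject to investigator judgement under criteria [14] and [32]. The documents give no probability of a baseline above 450 ms.
- **The post-baseline sentence may only fix a single baseline.** It does not say that predose readings enter the maximum, or to which treatment they would belong. The table shells, which SAP section 3 says hold the detail, are not among the documents reviewed. This makes the second point an ambiguity.

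A reader might also infer that a baseline-high subject is counted under every dose. The sequence tables rule that out for Japanese subjects, who receive two or three of five active regimens; only sequence 4 of Cohort 3 receives every dose used in its population. Nor does one predose reading among 13 mean that 1/13 of classifications are wrong: a subject is misclassified only if the predose change exceeds the cut-off and no postdose change does.

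**Conclusion.** The point holds as a low-cost improvement. Followed literally, SAP 9.4.5 can place a pre-existing QTcF above a threshold in lasmiditan columns, at 1/6 per column and in up to three columns, with nothing under placebo for the two placebo-free sequences. This rests on about 2 completers per sequence, on at least one baseline-high subject enrolling, and on the assumed SDs for how reliably that subject is counted.

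The documents do not support reading this as a contradiction or as a failure of the QT assessment. The SAP calls these counts postdose values and never treatment-emergent; no decision rule hangs on them; and SAP 9.4.9 plans no inferential safety analysis.

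The maximum-increase wording is secondary: under half a percentage point on the >30 ms count at SDs of 5 to 10 ms. Its value lies in preventing two programmers from building the table differently.

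**What to change.** Keep the stated baseline and amend SAP 9.4.5 in two places.

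1. For each of 450, 480 and 500 ms, count subjects whose baseline QTcF is at or below the threshold and who have a postdose value above it. Show in a separate row the number already above it at baseline.
2. Limit the >30 and >60 ms maximum increase to postdose time points of the period concerned.

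For the Cohort 2 sequence 4 example, the >450 ms entry at 200 mg, 400 mg and 2 x 200 mg would change from 1/6 to 0/5, with one subject in the separate row.

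The cost is SAP wording and a small programming change, with no new data. The drawback is that denominators can differ slightly by threshold. The fix also does not help with a subject just below a threshold at baseline: at a true mean of 448 ms, a crossing of 450 ms in a given period remains likely without any drug effect (step 3 of the working). The threshold table should therefore still be read beside the change table.
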